### **III. Recruitment Process:**

The clinical visit record for the Department of Orthopaedics will be screened for patients with osteoarthritis who generally meet the study requirements and who have a history of recurrent knee injections that have found clinical benefit. This patient population will be contacted via telephone to survey the need for another injection. If the patient requests to schedule a visit for injection, the research staff will inform the patient of the research opportunity. Once in the office, recruitment will take place in a private space during the clinic visit. Eligible patients who agree to participate in the study will be required to sign an Informed Consent Document prior to any study-specific procedures being done. After signing the Informed Consent, study Subjects are defined as "enrolled."

### **IV. Consent Process**

Once the potential participant has been contacted and is in the clinic, a member from the research team will explain the whole research study and answer all their questions in a private room in the clinic. Once everything has been explained to the potential participant, ensuring that they

comprehend everything in the consent document, and all the potential participant's questions have been answered, then the participant will be asked to sign the consent form. The participants will also be given a copy of the form they just signed to keep for themselves.

## **V. Inclusion/Exclusion:**

### Inclusion criteria:

1. Patients aged 40 and over, presenting with a knee disorder of at least one knee
2. Patients eligible for use of either corticosteroid or biological agent for treatment of moderate or severe (but not end-stage) knee osteoarthritis
3. KL grade of 2-3

### Exclusion criteria:

1. Subjects less than 40 years of age
2. Previous reconstructive knee surgery
3. Participating in another clinical trial
4. Unable to receive corticosteroid injections (i.e., allergies, adverse reactions, etc.)
5. Unable to sign informed consent
6. Pregnant or plan to become pregnant

## **VI. Number of Subjects:**

Approximately 70 participants will be enrolled. 35 to each arm if funding allows.

## **VII. Study Procedures/Methods:**

### Enrollment/Randomization/Treatment Visit:

Eligible patients with primary osteoarthritis in at least one knee will be enrolled on a voluntary basis. Prior to the injection, patient-reported outcomes will be quantified using a visual-analog scale (VAS) to assess pain level, a Knee Injury and Osteoarthritis Outcome Score-Joint Replacement (KOOS-JR), and UCLA Activity score to assess functional activity level as part of standard care. These results will be deidentified and analyzed in the laboratory.

The patient will be randomized into one of two treatment arms. If the patient has a history of receiving bilateral knee injections for osteoarthritis and meets study requirements, randomization will occur for both knees. Randomization will be employed using a computer-generated random assignment sequence and results kept in concealed envelopes. The participant will be blinded to the injection regime received.

Enrolled patients will be randomized to one of two treatment arms:

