**Deleted: ¶**

Treatment Groups	First Injection
------------------	-----------------

Steroid Group	Triamcinolone 40 mg/1 mL (Kenalog) injection with 5 mL of 1% lidocaine
PRP Group	Platelet-rich plasma

*Blinding:*

Syringes will be prepared and masked with opaque tape by the clinic nurses, thus providing blinding for subjects.

A specimen of serum (from ~5mL of whole blood) and urine will be collected from the subject. If the subject's knee is aspirated prior to the injection (as commonly practiced), the synovial fluid will be collected, as well. These specimens will be deidentified and analyzed in the laboratory.

If the subject is randomized to the PRP group, the remainder of the PRP mixture not injected into the knee will be deidentified and analyzed in the laboratory.

Follow-Up/Clinic Visits:

Subjects will be required to complete VAS, KOOS-JR, and UCLA activity score surveys at baseline, 2 weeks, 4 weeks, 8 weeks, 12 weeks, 6 months, and 1 year. At the 4-week follow-up visit, urine and blood specimens will be collected as they were at the baseline visit. Synovial fluid collection will occur at this time point by a knee aspiration procedure.

Clinic follow-up evaluations will include a general assessment of appearance, range of motion, and function. ~~If the subject schedules another clinic visit within the one-year study timeline, subjects will be unblinded to which treatment arm they had received. At this visit or any time after, if an injection is indicated by participant pain and functionality scores, the participant has the choice to receive steroid or PRP injection, based on preference. If subjects in the PRP study arm experience severe pain, it is recommended to follow up with their physician for assessment and possible rescue therapy with corticosteroid injection. At any point during the study, the subject has the right to request rescue surgery and may proceed to do so with physician approval.~~

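### The protocol is inconsistent on whether the patient or the knee is randomised, and so does not exclude PRP in one knee and steroid in the other

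*Protocol*

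**What the plan says.** Most of the protocol places arm membership at the level of the person. In section VII (Enrollment/Randomization/Treatment Visit) the general rule is "The patient will be randomized into one of two treatment arms", and the treatment table is introduced with "Enrolled patients will be randomized to one of two treatment arms". The blinding sentence there speaks of a single regime: "The participant will be blinded to the injection regime received". After the table, the handling of leftover PRP begins "If the subject is randomized to the PRP group" and refers to "the remainder of the PRP mixture not injected into the knee", that is, one subject, one group and one knee. The baseline visit list ties the first injection to the treatment arm, in the singular. Section VI counts people: "Approximately 70 participants will be enrolled. 35 to each arm if funding allows".

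One sentence, placed directly after the general rule, departs from this: "If the patient has a history of receiving bilateral knee injections for osteoarthritis and meets study requirements, randomization will occur for both knees".

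The primary objective concerns MCP-1 in serum, urine and synovial fluid. Serum and urine are sampled once per person at a visit: "A specimen of serum (from ~5mL of whole blood) and urine will be collected from the subject". The visit schedule repeats this at 4 weeks. The UCLA score describes the person's activity level.

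**The concern.** The bilateral sentence makes randomisation itself the thing that happens to both knees. If the patient's single allocation already settled the matter, it would have been enough to say that both knees are treated. Staff opening envelopes could reasonably draw once for the patient or once per knee, and could do so differently for different participants.

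If a participant ends up with one treatment in each knee, the 4-week serum and urine concentrations follow exposure to both products. They cannot be credited to PRP or to steroid, whether the analysis compares the arms (section II says the steroid arm is there for comparison) or looks at change after PRP (the primary objective). The same holds for UCLA. An analysis plan can exclude such participants or code their exposure as one half, but it cannot give them a single exposure once the injections have been made. The remedy therefore belongs at the allocation step, which the protocol fixes.

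**Working it through.** **1. The text side by side**

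| Place in protocol | Unit implied |
|---|---|
| Section VI, number of subjects | participant |
| Section VII, general randomisation rule, and its repeat before the treatment table | patient |
| Section VII, bilateral sentence | both knees; joint or separate allocation not stated |
| Section VII, PRP remainder | subject, one knee |
| Section VII, baseline visit list | one treatment arm |
| Section VII, serum and urine specimens | subject |

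No entry says that the two knees share an allocation, and none says that they are allocated separately.

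**2. Which data are exposed**

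Only participants with a different treatment in each knee are affected, and for them only the measures taken on the whole person: serum MCP-1, urine MCP-1 and UCLA. Synovial fluid comes from a particular knee and keeps its treatment label.

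**3. Size, as an illustration**

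From the protocol: 70 participants, 2 × 35. Section XIII mentions a power analysis but gives no inputs, so its figure cannot be reproduced here, and the argument does not depend on it. Assumed: bilateral share f of 10%, 20% or 30%; independent 1:1 allocation of each knee; two-sided 5% level; 80% power with all 70 participants.

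- Probability that two independently allocated knees differ: 2 × 0.5 × 0.5 = 0.5.
- Expected discordant participants: 70 × f × 0.5.
- Left per arm after excluding them: 35 × (1 − f/2).
- Standardised difference giving 80% power at 35 v 35 (two-sample t-test, noncentral t): 0.679.
- For a within-PRP change from baseline, participants exposed to PRP only: 35 × (1 − f) + 70 × f/4. Standardised change giving 80% power at n = 35 (one-sample t-test): 0.487.

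| f | Discordant of 70 | Left per arm | Power, between arms | PRP-only n | Power, within PRP |
|---|---|---|---|---|---|
| 10% | 3.5 | 33.25 | 77.9% | 33.25 | 77.8% |
| 20% | 7 | 31.5 | 75.6% | 31.5 | 75.5% |
| 30% | 10.5 | 29.75 | 73.1% | 29.75 | 72.9% |

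The normal approximation for the between-arm case (difference 0.670) gives 78.0%, 75.7% and 73.3%. Keeping the discordant participants with exposure coded 0, 0.5 or 1 recovers almost nothing: in simulation, power was about 78%, 75% and 73%. That coding also needs the assumption that the response lies midway between the two treatments.

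**4. Other allocation schemes**

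One allocation covering both knees gives no discordant participants and no loss. Deliberately giving opposite treatments to the two knees would make every bilateral participant discordant: 70 × f = 7, 14 and 21.

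**The case against.** The strongest reply is that the protocol already answers the question. The sentence just before the disputed one puts the patient in one arm. The same section repeats this, and sections VI and VII otherwise treat arm as a property of the person. Someone with a different treatment in each knee is not in one of two arms, so a coherent reading is one arm per patient, applied to both knees where both qualify. This stands in part. A reader might infer that the protocol prescribes, or positively permits, split-knee treatment. The documents do not support that: they say nothing either way, and the person-level wording points against it. What remains is that the bilateral sentence is the specific rule for this case, it can naturally be read knee by knee, and nothing rules that reading out.

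A reader might also infer a known loss of power. That is not supported either. The bilateral share, the planned power and the knee-allocation scheme are all unstated. Section III recruits patients with recurrent injections, which means repeated and not bilateral. Only the disputed sentence shows that bilateral patients are expected, and it does not say how many.

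Finally, how knee-level measures are analysed, including the choice of an index knee and allowance for correlation between knees, can properly be left to an analysis plan and is not part of this point. A knee-level design also has a merit: it would allow a within-person comparison in synovial fluid. It offers nothing comparable for serum and urine.

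**Conclusion.** The point holds as an internal inconsistency about the unit of allocation. On one natural reading of section VII, some participants would have serum and urine MCP-1 and UCLA values that belong to neither arm.

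The loss runs from nil, if one allocation covers both knees, to about 2 to 7 percentage points of power under independent knee allocation with a 10% to 30% bilateral share and a nominal 80%. Every input to that range except the 70 participants and the 35 per arm is an assumption. That the text leaves the question open is certain; which reading was intended, and how many participants it concerns, is not. This is a cheap improvement and not a threat to the trial as a whole.

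**What to change.** Amend the randomisation paragraph of section VII to say that the participant is the unit of randomisation, with one envelope and one allocation per participant covering any knee in the study. State in section VI that the 35 per arm are participants. Check that the envelope list has one entry per participant.

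The cost is an amendment of a sentence or two and a check of the list, with no extra patients. The design gives up a within-person comparison of PRP with steroid between knees. Sections II and VII describe the injection for a single knee in both arms, so the sponsor must also reconcile those passages with the treatment of bilateral participants; the current wording already raises that question.

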**Deleted: ¶**

Treatment Groups	First Injection
------------------	-----------------

Steroid Group	Triamcinolone 40 mg/1 mL (Kenalog) injection with 5 mL of 1% lidocaine
PRP Group	Platelet-rich plasma

*Blinding:*

Syringes will be prepared and masked with opaque tape by the clinic nurses, thus providing blinding for subjects.

A specimen of serum (from ~5mL of whole blood) and urine will be collected from the subject. If the subject's knee is aspirated prior to the injection (as commonly practiced), the synovial fluid will be collected, as well. These specimens will be deidentified and analyzed in the laboratory.

If the subject is randomized to the PRP group, the remainder of the PRP mixture not injected into the knee will be deidentified and analyzed in the laboratory.

Follow-Up/Clinic Visits:

Subjects will be required to complete VAS, KOOS-JR, and UCLA activity score surveys at baseline, 2 weeks, 4 weeks, 8 weeks, 12 weeks, 6 months, and 1 year. At the 4-week follow-up visit, urine and blood specimens will be collected as they were at the baseline visit. Synovial fluid collection will occur at this time point by a knee aspiration procedure.

Clinic follow-up evaluations will include a general assessment of appearance, range of motion, and function. ~~If the subject schedules another clinic visit within the one-year study timeline, subjects will be unblinded to which treatment arm they had received. At this visit or any time after, if an injection is indicated by participant pain and functionality scores, the participant has the choice to receive steroid or PRP injection, based on preference. If subjects in the PRP study arm experience severe pain, it is recommended to follow up with their physician for assessment and possible rescue therapy with corticosteroid injection. At any point during the study, the subject has the right to request rescue surgery and may proceed to do so with physician approval.~~

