### **Objectives:**

#### Primary objective:

- To evaluate the effect of intra-articular PRP injection upon serum, urine, and synovial fluid MCP-1 concentrations in knee OA patients
  - Previous studies have indicated that this inflammatory biomarker may be significantly decreased from baseline in the serum of knee OA patients after receiving intra-articular PRP injections, when measured three months after a patient's final injection. Monitoring fluid biomarker concentration provides insight into the joint environment and may correspond to clinical outcomes.

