#### Secondary objectives:

- To examine the effect of PRP injection upon serum, urine, and synovial fluid concentrations of additional pro-inflammatory biomarkers in knee OA patients
  - Other pro-inflammatory markers of interest in fluids of knee osteoarthritis patients include RANTES, IL-1b, IL-6, IL-8, TNF-a, MIP-1a, and PGE2. Each of these proteins plays a unique role in the inflammatory cascade and can provide insight into the inflammatory status of the joint.

- To evaluate the effect of PRP injection upon serum, urine, and synovial fluid concentrations of anti-inflammatory biomarkers in knee OA patients
  - In contrast, IL-1RA, IL-4, and IL-10 act through pathways to reduce inflammation. Measuring levels of these proteins affords increased insight into inflammatory status.
- To assess the effect of PRP injection upon serum, urine, and synovial fluid concentrations of other pro-degradative biomarkers in knee OA patients
  - Cartilage degradation by matrix metalloproteinases (MMPs) is a significant component of OA progression, and analysis of these enzymes is critical in understanding this component of OA pathophysiology.
- To evaluate the effect of PRP injection upon serum, urine, and synovial fluid concentrations of anti-degradative biomarkers in knee OA patients
  - TIMP-1 and TIMP-2 are proteins that inhibit degradation within the joint and are therefore relevant to the monitoring of OA progression.
- To examine the effect of PRP injection upon serum, urine, and synovial fluid concentrations of cartilage matrix proteins in knee OA patients
  - Collagen and proteoglycan are key components of the extracellular matrix of cartilage. Assessing COMP, CTX-I, CTX-II, PIICP, and HA concentrations provides further insight into the balance between anabolism and catabolism of these components.
- To assess differences in patient serum, urine, and synovial fluid biomarker concentrations between single- and double-PRP injections
- To evaluate the impact of PRP injection upon patient-reported outcome measures
- To evaluate relationships between baseline patient biomarker concentrations and treatment efficacy, based on patient-reported outcome measures, following PRP or corticosteroid injection

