**Deleted:**

The visits and all research activities are outlined below:

Baseline Visit:

- Consent/Randomization
- Objective Measures:
  - o Serum collection
  - o Urine collection
  - o Synovial fluid collection
  - o General assessments
- Subjective Measures:

- o VAS Pain
- o KOOS-JR
- o UCLA Activity
- Intervention:
  - o Initial injection based on treatment arm

2 Weeks (+/- 6 days) Surveys:

- Subjective Measures:
  - o VAS Pain
  - o KOOS-JR
  - o UCLA Activity

4 Weeks (+/- 1 week) Follow-Up:

- Objective Measures:
  - o Serum collection
  - o Urine collection
  - o Synovial fluid collection
  - o General assessments
- Subjective Measures:
  - o VAS Pain
  - o KOOS-JR
  - o UCLA Activity

8 Weeks (+/- 13 days) Surveys:

- Subjective Measures:
  - o VAS Pain
  - o KOOS-JR
  - o UCLA Activity

12 Weeks (+/- 2 weeks) Surveys:

- Subjective Measures:
  - o VAS Pain
  - o KOOS-JR
  - o UCLA Activity

6 Months (+/- 2 month) Surveys:

- Subjective Measures:
  - o VAS Pain
  - o KOOS-JR
  - o UCLA Activity

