### **VIII. Potential Risks:**

We do not expect any significant medical risks associated with the treatments presented in this study. Most of the risk associated with this study is related to piercing the skin by injection with synovial fluid collection and the venous blood draw. These can include the following: pain, bruising, bleeding, infection, and damage to surrounding structures, such as nerves and blood vessels. The risks of PRP injections include local infection and pain at injection site. The risks of corticosteroid injections include pain at injection site, skin discoloration, elevated blood sugar, infection, cartilage deterioration, and allergic reaction.

Synovial fluid collection in this study is part of the injection process and a stand-alone procedure at the 4-week visit. It has the same risk as the risk for injections listed previously. If there is a concern with the risks associated with the study, the participants are recommended to ask their provider for more information regarding the risks of the injection to their specific health condition. At any point, the participant has the right to withdraw from the study without recourse.

To help lower these possible risks, only professionally trained individuals will participate in the collection of the specimens. The participant will also be monitored for 5-10 minutes after injection.

All adverse events reported spontaneously by the participant or in response to questioning or observation by the investigator/research staff will be assessed for subject safety, acted upon as needed per situation and be recorded. If the events meet the criteria for IRB reporting, they will be reported to the IRB within five days.

Any adverse event associated with the intervention or deviation from the standard protocol will be evaluated related to subject safety and reporting requirements as well as any potential breach of confidentiality.

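### Baseline synovial fluid is conditional in one part of the protocol and scheduled for everyone in others, although synovial MCP-1 is in the primary objective

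*Protocol*

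**What the plan says.** The protocol describes synovial collection in several places.

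- **Section VII, treatment visit, specimen paragraph (after the blinding text).** Serum and urine are unconditional: "A specimen of serum (from ~5mL of whole blood) and urine will be collected from the subject". Synovial fluid is conditional: if the participant's "knee is aspirated prior to the injection (as commonly practiced), the synovial fluid will be collected, as well". This sentence is current text, not struck through.
- **Section VII, Baseline Visit list.** Introduced with "The visits and all research activities are outlined below", it lists synovial fluid collection next to serum and urine, with no condition.
- **Section VII, schedule table.** Synovial fluid collection is marked at the initial visit and at 4 weeks, without a footnote.
- **Section VIII, Potential Risks.** "Synovial fluid collection in this study is part of the injection process and a stand-alone procedure at the 4-week visit".
- **Section VII, Follow-Up/Clinic Visits, on 4 weeks.** "Synovial fluid collection will occur at this time point by a knee aspiration procedure".

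Two objectives in Section I depend on this sample. The primary objective is "To evaluate the effect of intra-articular PRP injection upon serum, urine, and synovial fluid MCP-1 concentrations in knee OA patients". One secondary objective is "To evaluate relationships between baseline patient biomarker concentrations and treatment efficacy, based on patient-reported outcome measures, following PRP or corticosteroid injection".

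**The concern.** The site has two rules for the same sample and no statement of which prevails. Under the specimen paragraph, whether a participant has a baseline synovial value depends on what happens at the injection and not on a protocol rule. The protocol does not say who decides to aspirate or on what grounds. It describes masking only for participants ("Syringes will be prepared and masked with opaque tape by the clinic nurses, thus providing blinding for subjects"), so it does not exclude a decision made with knowledge of the arm. That is a possibility, not a demonstrated bias.

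There are only two synovial time points, baseline and 4 weeks, and pre-injection fluid that was not drawn cannot be obtained later. No analysis plan can repair that. The consequences differ by objective:

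- **Primary objective, synovial part.** The 4-week values can still be compared by arm without a baseline, so missing baselines cost precision. Only an analysis of change from baseline would be restricted to the knees that were aspirated.
- **Baseline biomarkers and efficacy, synovial part.** The objective names no fluid. For synovial markers, a participant without a baseline sample has nothing to contribute, and a post-treatment value cannot stand in.
- **Serum and urine.** Unaffected.

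**Working it through.** **Whether the texts conflict.** The specimen paragraph treats synovial fluid differently from serum and urine. The visit list and the schedule table treat all three alike. The two rules give different instructions for a knee that would not otherwise be aspirated: under the first no sample is due, under the second one is. The conflict rests on the list and the table; Section VIII is weaker support, since it could also describe fluid taken when aspiration is done.

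**Inputs for the size of the effect.**
- From the protocol: about 70 participants, 35 per arm (Section VI). Section XIII gives no alpha, power, effect or SD, so the sample size itself cannot be reproduced.
- Assumed: two-sided 0.05 and 80% power; share with a baseline f = 1, 0.8, 0.6 or 0.5; correlation ρ between baseline and 4-week values of 0.5, with 0.3 and 0.7 as a range.

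**1. Arm comparison of 4-week values, no baseline used.** A two-sample t-test with 35 per arm detects 0.679 SD.

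**2. Same comparison with baseline adjustment, everyone kept.** A participant with a baseline carries 1/(1 − ρ²) units of information and one without carries 1, so

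MDE = 0.679 / √( f/(1 − ρ²) + 1 − f )

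For ρ = 0.5 and f = 0.5: 0.5/0.75 + 0.5 = 1.167, its square root is 1.080, and 0.679/1.080 = 0.629.

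| Share with baseline | ρ = 0.3 | ρ = 0.5 | ρ = 0.7 |
|---|---|---|---|
| 100% | 0.648 | 0.588 | 0.485 |
| 80% | 0.654 | 0.604 | 0.511 |
| 60% | 0.660 | 0.620 | 0.541 |
| 50% | 0.663 | 0.629 | 0.558 |

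**3. Change from baseline, unpaired participants dropped.** Pairs per arm are 35f. The t-test then detects, in SD of change:

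| Pairs per arm | Detectable difference |
|---|---|
| 35 | 0.679 |
| 28 | 0.762 |
| 21 | 0.886 |
| 17.5 | 0.976 |

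With equal SDs at both visits, the SD of change is SD × √(2(1 − ρ)), which equals the SD itself at ρ = 0.5. At that correlation these figures can be read against those in step 2.

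**4. Baseline synovial biomarker against efficacy, arms pooled.** By Fisher's z, detectable r = tanh( (1.960 + 0.842)/√(n − 3) ), and power at r = 0.33 is Φ( atanh(0.33) × √(n − 3) − 1.960 ), with atanh(0.33) = 0.343.

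| Baselines n | Detectable r | Power at r = 0.33 |
|---|---|---|
| 70 | 0.330 | 80% |
| 56 | 0.367 | 70% |
| 42 | 0.421 | 57% |
| 35 | 0.458 | 49% |

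The value 0.33 is a reference point: it is what 70 baselines detect at 80% power, not a target stated in the protocol.

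**The case against.** The strongest reply is that this is a wording mismatch with small consequences. A mark in a schedule table can stand for a sample taken if available, and the narrative can be read as qualifying the table. The protocol calls aspiration common practice, so the share aspirated may be high. On the figures above, the primary comparison loses only 0.04 SD at ρ = 0.5 with half the baselines missing. The larger losses need an analysis that drops unpaired participants, which the protocol does not specify. Knees that are not aspirated may be those with little fluid, so a required attempt may often yield nothing, and the 4-week tap may be dry as well. Both knees of some participants are randomized, so 35 per arm need not be the number of synovial samples.

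Much of this limits the size of the problem, and it is accepted:
- The aspiration share is unknown.
- Full baseline and 4-week collection is an upper bound.
- The primary loss is one of precision.
- Serum and urine still serve the baseline-biomarker objective.

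It does not remove the conflict. No footnote or other text makes the scheduled sample optional, and the visit list places it on the same footing as serum and urine. If nearly every knee is aspirated anyway, requiring the attempt costs almost nothing; if not, it prevents a loss that cannot be made good.

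**Conclusion.** The concern holds and should be fixed. Current text makes baseline synovial fluid conditional in one place and scheduled for everyone in others, for a fluid named in the primary objective.

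If the conditional rule is followed, the cost to the primary synovial comparison is modest provided everyone is kept: at most 0.07 SD in the range examined (0.49 to 0.56 SD at ρ = 0.7 with half the baselines missing). It is larger for a paired-only change analysis and for the synovial part of the baseline-biomarker objective. These sizes rest on assumed aspiration shares, correlations, alpha and power, and on 35 usable 4-week samples per arm. The textual conflict rests on none of them. The trial's serum and urine results are not in question.

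**What to change.** Replace the conditional sentence in the specimen paragraph of Section VII with wording such as:

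> Aspiration is attempted in every study knee immediately before the injection, in both arms. Any fluid obtained is collected, and its volume or a dry tap is recorded.

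This agrees with the visit list, the schedule table and Section VIII. Recording dry taps separates knees that gave no fluid from knees where no attempt was made, which the analysis will need to know.

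The cost is a one-sentence amendment and slightly longer injection visits. No visit is added, baseline collection is already scheduled for everyone, and its risks are already described in Section VIII. Dry taps will still leave some baselines missing.
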